9.9 Study Treatment Compliance

Administration of study drug will be performed under the supervision of the Investigator at the clinical site. The investigator will be at the clinical unit on the first day of dosing for each participant and will remain in the clinical unit for 8 hours (based on T_{max} data) post-dose for safety monitoring of the participants in the event an AE and/or SAE emerges.

Compliance with study drug is defined as the participant receiving 100% of the planned dosage. Drug administration will be recorded and any discrepancies with the dosing regimen must be documented and explained in the eCRF.

9.10 Treatment of Overdose

For this study, any dose of ATH-399A greater than the assigned dose for that cohort will be considered an overdose.

In the event of an overdose, the Investigator should:

- Evaluate the participant to determine, in consultation with the Medical Monitor, if possible, whether study treatment should be interrupted (Parts 1b and 2 only).
- Closely monitor the participant for any AE/SAE and laboratory abnormalities as medically appropriate and at least until the next scheduled follow-up.

9.11 Concomitant Therapy

Use of prescription or non-prescription drugs, herbal, and dietary supplements (including St. John's Wort) within 7 days (or 28 days if the drug is a potential hepatic enzyme inducer) or 5 half-lives (whichever is longer) prior to first dose administration and throughout the duration of study participation is prohibited for Part 1 of the study and Part 2 for participants aged 18-55 years, with the exception of paracetamol (acetaminophen) up to 2000 mg daily.

In Part 2 of the study, for the additional cohort of participants >55-80 years of age, the use of cholesterol medications, antihypertensives, hormone replacement therapy, asthma medications, thyroid medications, non-steroidal anti-inflammatory drugs, proton pump inhibitors, and antihistamines are permitted according to the medical judgement of the Investigator, as long as the participant is on a stable dose for at least 14 days prior to the first study drug dose. As needed, paracetamol up to 2000 mg per day is permitted.

Hormonal contraceptives may be allowed if deemed to not interact with the study drug PK.

Prune juice during mealtimes is allowed and will be provided by the clinic to treat constipation, if needed.

10 DISCONTINUATION OF STUDY TREATMENT AND PARTICIPANT DISCONTINUATION/WITHDRAWAL

Discontinuation of specific sites or of the study as a whole are detailed in [Section 13.1.10](#).

10.1 Study Stopping Criteria

In the event of a life-threatening or fatal AE, the SRC will urgently convene to assess the event and determine if it is related to study drug. In the meantime, all dosing must be suspended until a decision has been made by the CRS. If the determination is made that the AE is related to study drug, the study will be suspended. Continuation of the study would require approval by the appropriate regulatory authority(ies).

Data from any participant in the sentinel groups with significant safety issues will be reviewed by an ad hoc SRC, and all dosing must be suspended until a decision is made, prior to dosing the remaining non-sentinel participants in each cohort:

- One participant per cohort who receives ATH-399A experiences a SAE which is considered to be related to the study medication.
- Two participants per cohort who receive ATH-399A have QTc prolongation, defined as an average absolute (regardless of baseline value) QTcF >500 msec or an increase of QTcF > 60 msec above baseline, confirmed by repeating after 5 minutes, and determined post-dose.
- Two participants per cohort who receive ATH-399A exhibit hypotension, defined as resting supine diastolic blood pressure <40 mmHg persisting for at least 10 minutes on repeated assessment, or an asymptomatic or symptomatic fall in systolic blood pressure to below 80 mmHg, persisting for at least 10 minutes on repeated assessment.
- Two participants per cohort who receive ATH-399A exhibit hypertension, defined as an increase in resting systolic blood pressure to above 180 mmHg, persisting for at least 10 minutes, or an increase in resting diastolic blood pressure to above 105 mmHg, persisting for at least 10 minutes.
- Two participants per cohort who receive ATH-399A exhibit tachycardia, defined as resting supine heart rate >130 beats per minute, persisting for at least 10 minutes.
- Two participants per cohort who receive ATH-399A exhibit symptomatic bradycardia, defined as heart rate <40 beats per minute, or asymptomatic bradycardia, defined as resting supine heart rate <30 beats per minute while awake, persisting for at least 10 minutes, or clinically significant arrhythmia.
- One participant per cohort who receives ATH-399A exhibits abnormal liver tests defined as:
 - Aspartate aminotransferase (AST) or alanine aminotransferase (ALT) $>5X$ upper limit of normal (ULN).
 - AST or ALT $>3X$ ULN along with one of the following criteria:
 - total bilirubin level $>2X$ ULN or
 - international normalized ratio (INR) time $>1.5X$ ULN or

- the appearance of fatigue, nausea, vomiting, right upper abdominal pain or tenderness, fever, rash, and/or eosinophilia (>5%).
- Alkaline phosphatase (ALP) >3X ULN.
- ALP >2.5X ULN and total bilirubin >2X ULN.
- ALP >2.5X ULN with the appearance of fatigue, nausea, vomiting, right upper abdominal pain or tenderness, fever, rash, and/or eosinophilia (>5%).
- One participant per cohort who reaches a plasma AUC₀₋₂₄ of $\geq 1800 \text{ ng}^* \text{h/mL}$
- Two participants per cohort who receive ATH-399A exhibit renal toxicity, defined as serum creatinine $\geq 1.5 \text{X ULN}$ (confirmed by repeating within 24 hours).
- Two participants per cohort who receive ATH-399A exhibit hematologic toxicity, defined as one or more of the following (confirmed by repeating within 24 hours):
 - Leukocyte count $< 2.5 \times 10^9 / \text{L}$
 - Neutrophils $< 1.3 \times 10^9 / \text{L}$ and $< 1.0 \times 10^9 / \text{L}$ for Afro-American participants
 - Platelet count $< 75 \times 10^9 / \text{L}$

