4.2 Study Schema

Single Ascending Dose (SAD) Part 1a

[figure not shown]
Approximately 40 participants total.

5 cohorts, 8 participants each. Dosed in a fasted state.

Sentinels: 2 participants (1 ATH-399A, 1 placebo)

Non-sentinels: 6 participants (5 ATH-399A, 1 placebo)

The SRC will review PK data for up to 48 hours post-dose in at least 6 evaluable participants in order to make decision whether to escalate to the next planned dose level, decrease the next dose level, repeat a dose level, or not evaluate any additional dose.

SRC=Safety Review Committee

Part 1b (open-label, food effect)

[figure not shown]
12 participants total, crossover.

Sequences: AB, BA

Treatment A: Single dose of ATH-399A after a high-calorie, high-fat breakfast.

Treatment B: Single dose of ATH-399A after fasting.

[figure not shown]
Dose selection= depends on results from Part 1a.

Multiple Ascending Dose (MAD) Part 2

Approximately 16 participants (composed of 2 cohorts of 8 participants each) plus an additional cohort of 8 participants aged >55-80 years.

Dose selection= depends on results from Part 1a and 1b. Dosed in fasted state.

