9.7 Assignment to Study Treatment

Participants will be assigned sequentially to study part and cohort, and randomized within their assigned part/cohort of the study. Participants will be numbered during screening and study procedures according to the site SOP.

For each cohort in Parts 1a, 1b and 2, eligible participants for participation will be randomized (on Day 1) to receive either the active or placebo. Participants in Part 1a and Part 2 will be randomized in a 3:1 ratio, for a total of 6 participants per cohort receiving ATH-399A and 2 participants receiving the placebo in each dose level. In Part 1a, two sentinel participants will be dosed initially (1 active and 1 placebo). The remaining 6 participants (5 actives and 1 placebo) will be dosed at least 48 hours later after sentinels have been evaluated. Participants in Part 1b will be randomized in one of the 2 arms to receive study treatments in the sequence AB or BA. If PK data analyzed from Parts 1a and 1b demonstrate a potential accumulation of ATH-399A, a sentinel approach similarly used in Part 1a will be considered for the dosing of Part 2 where sentinels will be dosed on Day 1 and the remaining participants will be dosed at least 96 hours later, which would allow safety assessment of the sentinel subjects after steady-state has been attained. One randomization scheme will be produced for each cohort separately.

Participants may be automatically replaced if they withdraw/discontinue after randomization but prior to any dosing. Replacement of participants who withdraw/discontinue post dose will be at the discretion of the Sponsor. Procedures will be performed according to the site's SOP.

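### Seven of the ten sentinel-stage criteria in Protocol 10.1 need two ATH-399A recipients, but each sentinel pair has only one, so these seven cannot be met at that stage

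*Protocol*

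**What the plan says.** Protocol 10.1 opens with a suspension of all dosing for any life-threatening or fatal AE. It then turns to sentinels: "Data from any participant in the sentinel groups with significant safety issues will be reviewed by an ad hoc SRC". No one is dosed while that review is pending, and it comes before the rest of the cohort starts treatment. Ten criteria follow.

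- **Three need one participant:** related SAE, abnormal liver tests, and the AUC0-24 limit.
- **Seven need two ATH-399A recipients in the cohort:** QTc, hypotension, hypertension, tachycardia, bradycardia/arrhythmia, renal and hematologic. Examples are "Two participants per cohort who receive ATH-399A have QTc prolongation, defined as an average absolute (regardless of baseline value) QTcF >500 msec" and "Two participants per cohort who receive ATH-399A exhibit renal toxicity".

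The renal and hematologic items also require confirmation by a repeat within 24 hours.

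The make-up of the sentinel pair is consistent across the documents. Protocol 4.2 has "Sentinels: 2 participants (1 ATH-399A, 1 placebo") and then "Non-sentinels: 6 participants (5 ATH-399A, 1 placebo"). Protocol 9.7 and 9.8 and SAP 3.3.1 and 3.4 agree.

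Protocol 7.1.1 requires an Investigator and Medical Monitor discussion of the sentinel data before the other six are dosed, and makes that dosing conditional on no clinically significant safety issue. It also mentions a sentinel stopping rule. The 10.1 list is the only such rule visible in the documents.

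**The concern.** A sentinel step in a first-in-human study exists so that one clear toxicity in one person can hold back the rest of the cohort. The two-person counts in 10.1 match those in the cohort escalation list of 7.3, where six active recipients make a count of two attainable. The 10.1 list seems to have been adapted for a short window, because the liver sub-item for an elevation lasting more than two weeks appears in 7.3 but not in 10.1. The participant counts were not adapted.

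As written, one ATH-399A sentinel with a confirmed QTcF above 500 msec does not satisfy the listed QTc criterion. If the list defines a significant safety issue, that participant falls outside the definition. If the list is only illustrative, no stated threshold governs a single sentinel. On either reading, dosing of the five other ATH-399A recipients in that cohort depends on reviewers' judgement.

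**Working it through.** **Inputs.** The criteria and their counts come from Protocol 10.1. The sentinel and non-sentinel numbers come from Protocol 4.2 and 9.7 and SAP 3.3.1. Laboratory times come from Protocol Tables 1 and 3. Intervals to non-sentinel dosing come from Protocol 7.1.1 and 9.7 and SAP 3.3.1.

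**Step 1: cohort composition.** Active: 1 + 5 = 6. Placebo: 1 + 1 = 2. This reproduces the planned 6:2 split.

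**Step 2: count the criteria.** 3 (one participant) + 7 (two participants) = 10.

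**Step 3: can a two-person criterion be met?** With n active recipients dosed and per-person event probability p:

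- Sentinel stage, n = 1: P(at least 2) = 0 for every p, including p = 1.
- Sentinel stage with a one-person criterion: P(at least 1) = p.
- Full cohort, n = 6: P(at least 2) = 1 − (1−p)^6 − 6p(1−p)^5. For illustrative p this is 0.033 at 0.05, 0.114 at 0.10, 0.580 at 0.30 and 0.891 at 0.50.

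A count of two therefore works in 7.3 and cannot work in the sentinel list.

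**Step 4: timing of the confirmatory repeat (renal and hematologic only).** Part 1a safety laboratory draws before non-sentinel dosing are at 8 h, Day 2 (taken as 24 h) and Day 3 (taken as 48 h). Adding up to 24 h, repeats finish by 32 h, 48 h and 72 h.

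- Part 1a, Protocol interval (48 h, all cohorts): only the Day 3 draw is affected, by up to 72 − 48 = 24 h.
- Part 1a, SAP interval: 48 h for Cohorts 1–3, so the same 24 h gap. For Cohorts 4–5 it is 96 h, and 72 < 96, so no gap.
- Part 2, if sentinels are used: Protocol 9.7 gives at least 96 h. Draws before then are at 8 h and Day 2, so repeats finish by 32 h and 48 h. No gap.

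**Step 5: cost of a one-sentinel rule.** SRC review starts blinded, so either sentinel could prompt it. Let q be the background chance that a sentinel crosses any of the seven thresholds. The documents give no value, so q = 0.01 to 0.05 is assumed.

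- Part 1a, 5 × 2 = 10 sentinels: expected extra reviews 10q = 0.10 to 0.50. Chance of at least one, 1 − (1−q)^10 = 9.6% to 40.1%.
- All eight cohorts (five in Part 1a, three in Part 2), 16 sentinels: 16q = 0.16 to 0.80. Chance of at least one, 1 − (1−q)^16 = 14.9% to 56.0%.

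For a given q these are upper bounds, because some crossings would be reviewed anyway as significant safety issues. They measure the cost of the fix, not harm under the current text.

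**The case against.** The strongest reply is that a single sentinel event can already stop dosing, by four routes:

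- The lead-in to 10.1 speaks of any sentinel participant with a significant safety issue.
- The opening paragraph of 10.1 suspends all dosing for one life-threatening or fatal event.
- A serious, related form of any of the seven toxicities meets the SAE item with a count of one, and the SAE definition in 13.3.2 covers important medical events.
- The review in 7.1.1 is required in every Part 1a cohort and does not wait for a criterion to be met.

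In addition, 13.1.5.1 has the SRC meet on safety signals, and its separate Charter, not available here, may hold a one-sentinel rule.

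All of this stands. A reader might infer that the sentinel step has no effective hold, or that a sentinel with QTcF above 500 msec would be ignored. The documents do not support either inference, and reviewers would probably hold dosing. What survives is narrower: none of these routes applies the seven listed thresholds to one sentinel.

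Two further limits are fair. The seven items are not purely numeric, because the bradycardia item includes clinically significant arrhythmia, which has no number and falls directly under the 7.1.1 condition. Also, a replacement for an already dosed sentinel would receive the same treatment (SAP 3.6) and could give a second active sentinel. That is at the Sponsor's discretion and is not the planned design.

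**Conclusion.** The point holds for the text of Protocol 10.1. Seven of ten criteria cannot be met with one ATH-399A sentinel. This is a count and needs no assumption beyond the planned 1:1 pair. The practical effect is limited to a cohort whose active sentinel crosses one of the seven thresholds, where dosing of five further ATH-399A recipients rests on judgement. How often such an event would go unheld cannot be estimated from the documents, and the Charter may reduce the effect. The text should be corrected, but this is not evidence that participants are unprotected.

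The confirmation timing is a secondary point for Part 1a only. A reader might infer a gap throughout the study, but Step 4 confines it to the Day 3 draw: in Cohorts 1–3, and in Cohorts 4–5 only if the Protocol's 48 h is followed rather than the SAP's 96 h. Protocol 9.7 also makes dosing follow evaluation of the sentinels. It does not say whether an unconfirmed value counts as evaluated.

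**What to change.** 1. In the 10.1 sentinel list, replace the two-recipient count with one sentinel participant receiving ATH-399A for the seven criteria. Keep two in 7.3.
2. State that a crossing in either blinded sentinel prompts SRC review, with any unblinding under the existing 7.3 clause. Cross-reference that clause in 9.8, which otherwise restricts individual unblinding.
3. Use the same counts in Part 2 if sentinels are used.
4. For Part 1a, hold non-sentinel dosing until the repeat of a Day 3 creatinine or hematology value that crosses its threshold is available. Reconcile the 48 h and 96 h intervals for Cohorts 4–5 between Protocol and SAP. Part 2 needs no such timing rule.
5. If the SRC Charter already has a one-sentinel rule, carry it into 10.1.

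The cost is a short amendment or clarification and no extra participants. There would be the few additional ad hoc reviews sized in Step 5, each with a brief pause. A pending Day 3 repeat would delay dosing by up to about 24 h plus laboratory turnaround. Unblinding one sentinel also reveals the other's treatment, because the pair is 1:1.

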10.2 Discontinuation of Study Treatment

In rare instances, it may be necessary for a participant to permanently discontinue study treatment. If study treatment is permanently discontinued, the participant should, if at all possible, remain in the study to be evaluated for safety. See the SoA for data to be collected at the time of discontinuation of study treatment and follow-up and for any further evaluations that need to be completed.

10.3 Participant Discontinuation/Withdrawal from the Study

- A participant may withdraw from the study at any time at the participant's own request for any reason (or without providing any reason).
- A participant may be withdrawn at any time at the discretion of the Investigator for safety, behavioral, significant protocol deviations, or compliance reasons.
- A participant may be withdrawn at any time for positive pregnancy test, drug screen, cotinine test, or alcohol breath test.
- At the time of discontinuing from the study, if possible, an early termination visit should be conducted, as shown in the SoA. The participant will be permanently discontinued from the study treatment and the study at that time.
- If the participant withdraws consent for disclosure of future information, the Sponsor may retain and continue to use any data collected before such a withdrawal of consent.
- A PK blood draw may be collected at the time of withdrawal.

10.4 Lost to Follow-up

A participant will be considered lost to follow-up if the participant repeatedly fails to return for scheduled visits and is unable to be contacted by the study site.

The following actions must be taken if a participant fails to return to the clinic for a required study visit:

- The site must attempt to contact the participant and reschedule the missed visit as soon as possible, counsel the participant on the importance of maintaining the assigned visit schedule and ascertain whether the participant wishes to and/or should continue in the study.
- Before a participant is deemed lost to follow-up, the Investigator or designee must make every effort to regain contact with the participant (where possible, 3 telephone calls, followed by a certified letter to the participant's last known mailing address or local equivalent methods). These contact attempts should be documented in the participant's study record.
- Should the participant continue to be unreachable, the participant will be considered to have withdrawn from the study.

11 STUDY ASSESSMENTS AND PROCEDURES

- Study procedures and their timing are summarized in the SoAs ([Table 1](#), [Table 2](#), and [Table 3](#)).
- All screening evaluations must be completed and reviewed to confirm that potential participants meet all eligibility criteria. The Investigator will maintain a screening log to record details of all participants screened and to confirm eligibility or record reasons for screening failure, as applicable.
- Procedures conducted as part of the participant's routine clinical management and obtained before signing of the Informed Consent Form (ICF) may be utilized for screening or baseline purposes provided the procedures met the protocol-specified criteria and were performed within the timeframe defined in the SoA.
- In the event of a significant study-continuity issue (eg, caused by a pandemic), alternate strategies for participant visits, assessments, medication distribution and monitoring may be implemented by the Sponsor or the Investigator, as per local health authority/ethics requirements.
- At time points when vitals, ECGs, and blood collections coincide, the order for conducting assessments should be ECGs first, then vital signs, and then blood sample collection. Sample collections done outside the pre-defined time windows will not be considered as protocol deviations since actual post-dose sampling times will be used for PK and statistical analyses. Actual collection times should be recorded on the eCRF.
- Blood and urine samples will be collected and processed as per the Analytical Methodology Information Sheet.

Repeat or unscheduled samples may be taken for safety reasons or for technical issues with the samples. The maximum amount of blood collected from each participant over the duration of the study, including that collected for eligibility and safety purposes and any extra assessments that may be required, will not exceed 250 mL for Part 1a and 350 mL for Parts 1b and Part 2.

11.1 Informed Consent

Voluntary written informed consent must be obtained before any study procedures are performed, in accordance with International Council for Harmonisation (ICH) guidelines and requirements of informed consent (Title 21 CFR Parts 50.20 and 50.25) ([Section 13.1.3](#)).

11.2 Height, Weight, and BMI

Height (cm) and weight (kg) will be collected at the time points specified in the SoAs ([Table 1](#), [Table 2](#), and [Table 3](#)). Based on these, body mass index (BMI) will be calculated.

11.3 Demographics

Participant demographics will be obtained during screening and include sex, date of birth, race, and ethnicity.

11.4 Medical History

A complete medical and surgical history will be obtained during screening by the Investigator or a qualified designee. Surgical and medical history of current and clinically significant conditions will be recorded.

11.5 Prior and Concomitant Medications and Treatment Medications

The Investigator or qualified designee will review past and current medication use. All medications taken by the participant within 3 months of signing the ICF through the Follow-up Visit, including prescription medications, over-the-counter medications, vitamins, herbal therapies and supplements will be recorded. Hormonal contraceptives may be allowed if deemed to not interact with the study drug PK. Treatment Medications are medications used for the treatment of SAEs.

11.6 Safety Assessments

Planned timepoints for all safety assessments are provided in the SoA ([Table 1](#), [Table 2](#), and [Table 3](#)).

11.6.1 Physical and Neurological Examinations

A complete physical examination will be performed at screening, at the admission and at the discharge and will include assessments of the following: head, eyes, ears, nose, throat (HEENT), neck, chest, lungs, abdomen, musculoskeletal, dermatological, cardiovascular/peripheral vascular, and general neurological examination.

A brief physical examination will be performed at all other times, and will include assessments of the following: HEENT, chest, lungs, abdomen, dermatological, cardiovascular/peripheral vascular, and areas of note elicited from the participant.

